3.0 OBJECTIVES/AIMS

Study Objectives

Primary: To evaluate the hemodynamic effectiveness of Ang II (Giapreza) for intraoperative and postoperative hypotension in kidney transplant patients. This will be evaluated by the time to reaching BP goal.

Secondary: To evaluate the safety of Ang II (Giapreza) for intraoperative and postoperative hypotension in kidney transplant patients. This will be evaluated by collecting the incidence of common adverse events (ADE) seen from other Ang II (Giapreza) studies in this patient population.

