5.0 ENROLLMENT

The patients at the top of the adult kidney transplant list awaiting DDKT maintained by UIHHSS Transplant will be used to screen for eligibility. See addendum for Eligibility Checklist. Study personnel will perform the screening. A password protected Microsoft Excel sheet will be provided by the Transplant team at UIHHSS. This sheet will have the MRN for the top patients on the kidney transplant list. If patients are initially eligible via inclusion and exclusion review, they will remain on the password protected Microsoft Excel sheet. If they are not eligible, they will be removed after screening by one of the study personnel. This password protected Microsoft Excel sheet will be maintained on the "H" drive behind the University firewall maintained by the CCTS. It is estimated that 40 subjects will be consented/enrolled in order for 20 patients to receive study drug. Twenty patients are the goal for this study and no more than 20 patients will receive study drug.

All eligible study subjects will receive a Research Letter (see addendum for Research Letter) via the mail. One week after the Research Letter is mailed, the subjects that have not called the primary investigator regarding the study will be called via telephone by study personnel to follow-up and provide any additional information regarding the study. This call is to provide information regarding the study, study enrollment criteria, and answer any questions regarding the study. This call is informational only.

If a kidney transplant is offered to the previously contacted subjects the study personnel will be contacted by the Transplant Coordinator when the kidney transplant is confirmed. Once that subject arrives at UI Health for their transplant, subjects will be approached by study investigators in-person, reminded of the study criteria, have ample time to review study information again and the informed consent document, and will be asked to provide signed consent after the appropriate informed consent process is completed. Researchers participating in the consent process will review the informed consent document (ICD) with the recruited subject in its entirety ensuring the subject understands the research purpose, all risks/benefits and the study components of this research.

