6.0 STUDY DESIGN AND PROCEDURES

This will be a single-center, prospective, observational study.

The prospective, observational study will include 20 consecutive patients receiving DDKT requiring intraoperative or postoperative vasopressors to assess the hemodynamic efficacy and safety and efficacy of Ang II (Giapreza).

The care process for this study of Ang II (Giapreza) in deceased donor kidney transplants (DDKT) at University of Illinois Hospital and Health Sciences (UIHHSS) will follow the exact same procedure as described above except (in bold and red):

PRE-TRANSPLANT – n/a DURING TRANSPLANT

- The transplant operation begins.
- If intraoperative hypotension occurs (e.g. SBP < 120 mmHg) the attending surgeon and attending anesthesiologist will:
 - Give blood products first if patient bleeding
 - If not bleeding or hypotensive despite blood products, intravenous fluids will be given
 - If hypotensive despite intravenous fluids then the attending surgeon and attending anesthesiologist will assess for cardiogenic shock and if suspected give inotropes
 - If not in cardiogenic shock and hypotensive despite fluids (+/- inotropes) then Ang II (Giapreza) will be initiated as the first vasopressor given for the treatment of distributive shock.
 - Ang II (Giapreza) will be titrated intraoperative to achieve goal BP.
 - Ang II (Giapreza) will be initiated following the FDA approved dosing in the package insert. This dosing includes a starting dose of 20 nanograms ng/kg/min. Titration will occur every 5 minutes by increments of up to 5 ng/kg/min as needed. During the first 3 hours, the maximum dose will not exceed 80 ng/kg/min. Maintenance dose will n exceed 40 ng/kg/min. Administration through a central venous line will be recommended.
 - If the maximum dose of AT II (Giapreza) is reached (80 ng/kg/min in the first 3 hours or 40 ng/kg/min thereafter), additional vasopressor selection and management will be at the discretion of the attending surgeon and attending anesthesiologist.
 - If additional vasopressors are needed beyond Ang II (Giapreza), all other vasopressors will be titrated off first.
 - If the patient is unable to be titrated off the Ang II (Giapreza) intraoperatively, they will be continued postoperatively in the Intensive Care Unit (ICU) and titrated until the patients' blood pressure is stable without vasopressor support.
- If distributive shock does NOT occur intraoperatively, Ang II (Giapreza) will NOT be initiated.

AFTER TRANSPLANT

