- If the patient is unable to be titrated off the Ang II (Giapreza) intraoperatively, they will be continued
 postoperatively in the Intensive Care Unit (ICU) and titrated until the patients' blood pressure is stable
 without vasopressor support.
- If the patient never received Ang II (Giapreza) intraoperatively and postoperative hypotension occurs (e.g. SBP < 120 mmHg) the attending surgeon or ICU team will:
 - Give blood products first if patient bleeding
 - If not bleeding or hypotensive despite blood products, then intravenous fluids will be given

- If hypotensive despite intravenous fluids then the attending surgeon and attending anesthesiologist will assess for cardiogenic shock and if suspected give inotropes
- If not in cardiogenic shock and hypotensive despite fluids (+/- inotropes) then Ang II (Giapreza)
 will be given as the first line vasopressor for the treatment of distributive shock.
- Ang II (Giapreza) will be titrated postoperatively to achieve goal BP and titrated until the patients' blood pressure is stable without vasopressor support.
 - Ang II (Giapreza) will be initiated following the FDA approved dosing in the package insert. This dosing includes a starting dose of 20 nanograms ng/kg/min. Titration will occur every 5 minutes by increments of up to 5 ng/kg/min as needed. During the first 3 hours, the maximum dose will not exceed 80 ng/kg/min. Maintenance dose will n exceed 40 ng/kg/min. Administration through a central venous line will be recommended.
 - If the maximum dose of AT II is reached (80 ng/kg/min in the first 3 hours or 40 ng/kg/min thereafter), additional vasopressor selection and management will be at the discretion of the attending surgeon and attending anesthesiologist.
 - If additional vasopressors are needed beyond Ang II (Giapreza), all other vasopressors will be titrated off first.
 - If at any point the treating physician feels there is a safety concern with the study drug it can be discontinued immediately.
- Ang II (Giapreza) and other vasopressor medications (if applicable) will be titrated
 postoperatively to achieve goal BP and titrated until the patients' BP is stable without
 vasopressor support.
- If distributive shock does NOT occur postoperatively, Ang II (Giapreza) will NOT be initiated

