The study drug will be provided by La Jolla Pharmaceuticals for this study but they are not the study sponsor or providing any other financial support. Drug distribution will be managed by the Investigation Drug Service (IDS) at UI Health who has the capacity to retain all of the study drug in appropriate temperature-controlled settings. IDS will be used as this is a novel medication, not yet on formulary at UIHHSS, and this is a research investigation. They will maintain and dispense the medication for each kidney transplant in which subjects have consented in the event that vasopressors are required. Additionally, the medication will be ordered via Cerner/EPIC as a study medication and will be programmed into the Alaris pumps to be dosed via the dosing protocol listed above. Ang II (Giapreza) will not be used outside of the study protocol at our institution and will only be available under the electronic study order. Verifying pharmacists will be in-serviced regarding the study protocol and will be aware that this medication is only available and should be dispensed under the study order and as such not used in other contexts.

FOR STUDIES THAT COLLECT EXISTING OR PROSPECTIVE DATA

Health and laboratory data will be extracted manually from the electronic medical records (i.e. Cerner or Epic) for both arms of the study. Data will be prospectively captured over the course of 3 months after study initiation (i.e. using Ang II (Giapreza) for vasopressor management during kidney transplant) for the pilot. The data will be collected and input into a Redcap database for analysis. Data analysis will be performed using Spss.v25 computer software. Data collection will include the variables below.

Baseline characteristics:

-Age (years of age at the time of transplant)

- -Gender (M/F)
- -Race
- A) White
- B) Black
- C) Asian
- D) Hispanic
- E) Other
- -Weight (kilograms at time of transplant)
- -Height (centimeters at time of transplant)
- -Body mass index (kg/m² at time of transplant)
- -Duration of time on hemodialysis (years)
- -Donor baseline serum creatinine (mg/dL)
- -Warm/cold ischemia time (hours)
- -KDPI
- -Baseline systolic/diastolic/mean arterial pressure (mmHg)
- -Baseline heart rate (HR)
- -Comorbidities
- A) Hypertension
- B) Hyperlipidemia
- C) Heart failure with preserved ejection fraction
- D) Arrhythmias
 - -Atrial fibrillation
 - -Other
- E) Peripheral vascular disease
- F) Coronary artery disease
- G) Pulmonary hypertension
- H) Diabetes

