- -Type I
- -Type II

Intraoperative Hemodynamic Data Points:

- -Intraoperative BP (SBP, DBP, MAP) every 5 minutes
- -Intraoperative heart rate every 5 minutes
- -Maximum dose of Ang II (Giapreza) (ng/kg/min)
- -Duration of Ang II (Giapreza) (hours)
- -Number of intraoperative vasopressors (if applicable)
- -Intraoperative agents used in addition to Ang II (Giapreza) (if applicable)
- -Dopamine (Y/N)
- -Norepinephrine (Y/N)
- -Epinephrine (Y/N)
- -Phenylephrine (Y/N)
- -Vasopressin (Y/N)
- -Minimum intraoperative SBP and DBP (mmHg)
- -Minimum intraoperative HR (bpm)

- -Intraoperative volume resuscitation (L)
- -Type of crystalloid and volume: 0.9% NaCl, PlasmaLyte, Lactated Ringers (L)
- -Type of colloids and volume: Albumin, Hydroxyethyl Starch, Mannitol (L)
- -Intraoperative blood product utilization (volume and type of blood products administered)

Post-operative Hemodynamic Data Points:

- -Postoperative BP (SBP, DBP, MAP mmHg) every 1 hour for the first 72 hours or duration of vasopressors (whichever is longer) after transplant
- -Postoperative HR (bpm) every 1 hour for first 72 hours or duration of vasopressors (whichever is longer) after transplant
- -Maximum dose of postoperative Ang II (Giapreza) ng/kg/min
- -Maximum dose of postoperative other vasopressors (in norepinephrine equivalents if applicable)
- -Starting dose of postoperative Ang II (Giapreza) and other vasopressors (in norepinephrine equivalents if applicable)
- -Duration of postoperative vasopressors (hours if applicable)
- -Number of postoperative vasopressors (if applicable)
- -Minimum postoperative BP (SBP, DBP, MAP mmHg) in first 72 hours after transplant (in first 24hrs, second 24hrs, third 24 hrs, and total 72hrs)
- -Minimum postoperative HR (bpm) in first 72 hours after transplant (in first 24hrs, second 24hrs, third 24 hrs, and total 72hrs)
- -Maximum postoperative BP (SBP, DBP, MAP mmHg) in first 72 hours after transplant
- -Maximum postoperative HR (bpm) in first 72 hours after transplant
- -Postoperative agents used:
- -Dopamine
- -Norepinephrine
- -Epinephrine
- -Phenylephrine
- -Vasopressin
- -Postoperative volume resuscitation (L in the first 24hrs, 48hrs, 72hrs)
- -Daily intake volume (milliliters) during ICU admission
- -Daily urine output volume (milliliters) during ICU admission
- -Postoperative blood product utilization (volume and type of blood products administered during ICU admission after operating room)

Post-operative Clinical Data Points:

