9.0 DATA ANALYSIS

Statistical Analysis:

Continuous data -> Student t-test

Ordinal data -> Wilcoxon-Mann Whitney test

Nominal data -> Chi-square or Fisher's exact test

Multivariate regression analysis for factors associated with duration of vasopressors and worse kidney outcome

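### Section 9.0 lists group-comparison tests for a single Ang II cohort with no defined comparator, and as written none of them yields the primary endpoint, time to BP goal

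*Combined protocol and SAP*

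**What the plan says.** **Endpoint.** Section 3.0 makes hemodynamic effectiveness the primary objective: "This will be evaluated by the time to reaching BP goal". Safety is secondary there, whereas Section 1.0 names safety and hemodynamic effects together as the primary objective. No section gives the BP goal as a number. The systolic value of 120 mmHg in Sections 2.0 and 6.0 is an example of the hypotension that starts treatment, not a stated target.

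**Design.** Section 6.0 describes "20 consecutive patients receiving DDKT requiring intraoperative or postoperative vasopressors", with Ang II as first vasopressor. Section 5.0 caps the cohort: "Twenty patients are the goal for this study and no more than 20 patients will receive study drug". Under Sections 6.0 (Data Management) and 8.0, consented patients who are not treated contribute no data. A second arm is mentioned once, in Section 6.0, where data are to be extracted "for both arms of the study". It is not defined anywhere.

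**Analysis.** Section 9.0 has four lines: "Continuous data -> Student t-test", Wilcoxon-Mann-Whitney for ordinal data, chi-square or Fisher's exact for nominal data, and a multivariate regression on vasopressor duration and worse kidney outcome. Section 12.0 adds that the sample is one of convenience, without a calculation.

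**Events on the way to goal.** At maximum Ang II dose, "additional vasopressor selection and management will be at the discretion of the attending surgeon and attending anesthesiologist". The postoperative list adds: "If at any point the treating physician feels there is a safety concern with the study drug it can be discontinued immediately".

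**Data rules.** Section 6.0 plans "Intraoperative BP (SBP, DBP, MAP) every 5 minutes", but hourly readings after surgery. Section 6.0 (Data Management) has data extracted for every consented patient who receives Ang II. Section 11.0 says that a withdrawn patient's data are neither collected nor used.

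**The concern.** The listed tests compare groups, and the documents describe one group. A t-test or Wilcoxon-Mann-Whitney test on time to goal needs a second group, a reference value or a paired measurement, and none is named. The regression concerns other outcomes. The plan therefore commits the investigators to no particular primary result, and the method could be chosen after the data are seen.

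The choice matters most for patients who never reach goal. If they are left out because they have no time to analyse, Ang II looks faster than it was. The withdrawal rule and the two BP recording intervals could also shift the result.

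**Working it through.** **The plan's one sizing figure.** Sections 5.0 and 13.1 expect 40 consented patients for 20 treated, and Section 13.1 assumes about 50% vasopressor use. 40 × 0.50 = 20, so the figure reproduces. There is no alpha, power or effect size to check.

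**Each line of Section 9.0 against the endpoint.**
- Two-sample t and Wilcoxon-Mann-Whitney: up to 20 patients in one group and no defined second group, so no test statistic exists.
- One-sample t: no reference value is given.
- Paired t: time to goal has no baseline value to pair with.
- Chi-square or Fisher: no groups are named, and time is not nominal.
- Regression: its outcomes are vasopressor duration and kidney outcome.

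None yields time to BP goal.

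**Non-attainers.** Assume that a proportion s reach goal, with exponential times among those who do. The all-patient median solves s(1 − e^(−λt)) = 0.5, and the responders' median is ln 2/λ. The ratio is −ln(1 − 0.5/s)/ln 2.

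| s | Ratio | All-patient median if responders' median is 10 min |
|---|---|---|
| 0.90 | 1.17 | 11.7 |
| 0.75 | 1.58 | 15.8 |
| 0.60 | 2.58 | 25.8 |

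**Added vasopressors.** With the Section 6.0 titration figures, maximum dose is reached at the earliest after (80 − 20)/5 = 12 steps × 5 min = 60 min. A rule for vasopressors added at that point would not move the medians in the table. It would affect the final proportion and the late times.

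**Withdrawal.** Start from an assumed 15/20 = 75% at goal (exact 95% CI 50.9% to 91.3%) and remove withdrawn patients.

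| Withdrawn | All non-attainers | All attainers |
|---|---|---|
| 1 | 15/19 = 78.9% | 14/19 = 73.7% |
| 2 | 15/18 = 83.3% | 13/18 = 72.2% |
| 3 | 15/17 = 88.2% | 12/17 = 70.6% |

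The bias can run either way. Because of the cap, a treated patient who withdraws cannot be replaced once 20 have been treated.

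**BP grid.** If readings fall every g minutes with random alignment and BP stays at goal, a true attainment at time t is first seen on average at t + g/2. For t = 10: 10 + 5/2 = 12.5 min in surgery and 10 + 60/2 = 40 min afterwards.

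**What 20 patients can support.** Rank non-attainers last. The 6th to 15th ordered times give a distribution-free interval for the median with 95.9% coverage. For safety, the exact two-sided 95% upper limit after no events is 1 − 0.025^(1/n): 16.8% for 0/20, and 30.8% for 0/10 if, say, only 10 start in surgery and are at risk of intraoperative arrhythmia.

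**Regression.** With k pure-noise covariates and n = 20, expected R² is k/(n − 1). For k = 2, 5 and 10 this is 2/19 = 0.11, 5/19 = 0.26 and 10/19 = 0.53. No covariates are named.

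**The case against.** The strongest defence is that this is a small convenience pilot, the tests may be meant for splits within the cohort, and a sensible investigator would report a median anyway. Pilot status explains the absent power calculation. It does not supply an estimator for the stated endpoint, and a within-cohort split, none of which is named, would not give the cohort's time to goal.

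Several stronger readings are tempting, and the documents do not support them.
- *That data from anyone outside the cohort are ruled out.* Only untreated and non-consenting patients are excluded. The reference to two arms stands under a heading that also covers existing data, and Section 2.0 hypothesises benefit over standard care. A historical comparator is undefined, not forbidden.
- *That the withdrawal rule must flatter Ang II.* No withdrawal rate or link to response is given, and the table shows both directions. Section 11.0 describes the consequence of withdrawal as losing access to the drug, which also fits withdrawal before dosing.
- *That hourly charting will distort the endpoint.* The plan does not say that time to goal comes from the hourly readings. Postoperative titration is every 5 minutes, so finer readings may exist.
- *That the safety endpoints lack only intervals.* Incidences are named in Sections 6.0 and 11.0, but pH is listed as values, if available, with no event definition.

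A full competing-risks analysis would also be more than 20 patients need. A median, a count of non-attainers and an exact interval meet the core requirement.

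**Conclusion.** The point holds, limited to the plan as written. The listed methods do not fit the only design that the documents define, and none produces the Section 3.0 primary endpoint. Section 1.0's joint safety and hemodynamic objective does not remove the gap, but the two statements need reconciling.

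The must-fix rating covers the missing primary analysis and the missing rule for non-attainers. The size of the second depends on attainment: a 1.17-fold shift in the median at 90% is modest and 2.58-fold at 60% is large. Both rest on assumed attainment rates and exponential times. Withdrawal is a real contradiction between Sections 6.0 and 11.0 but of unknown size and direction. The grid effect is conditional on using only the scheduled readings. Those two, with safety precision, the undefined second arm and the regression, are secondary.

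**What to change.** 1. Replace the two-group tests as the main analysis with single-arm estimation in all treated patients: time from Ang II start to a BP goal that the investigators state as a number, with non-attainers kept in the denominator. Report the median with 95% CI if reached, and the proportion at goal with exact 95% CI. Align the primary objective in Sections 1.0 and 3.0.
2. State in advance how added vasopressors and early stopping of Ang II are counted.
3. Report intraoperative and postoperative starters separately as well as overall. Use the finest charted BP after infusion start, or treat times as interval-censored if only hourly readings exist.
4. Reconcile Section 6.0 (Data Management) with the withdrawal rule in Section 11.0, subject to the consent terms, and report how many treated patients withdrew.
5. Give exact 95% CIs for safety incidences on their stated denominators. Define an event for pH or report it descriptively.
6. Delete or define the second arm, limit conclusions to non-comparative statements, and label within-cohort tests and the regression exploratory.

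No extra patients are needed. The cost is SAP wording, collection of clock times for Ang II start and stop and for any added vasopressor (Section 6.0 lists doses, durations and agents but not these times), and a possible protocol or consent amendment for item 4. Intervals will be wide within starter groups: 8/10 gives 44.4% to 97.5%. The reported time to goal may look less favourable.

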10.0 QUALITY CONTROL AND QUALITY ASSURANCE

All personnel collecting data will be taught where to obtain the most accurate information from Cerner and Epic to capture the desired data points. After the first subject of the pilot is enrolled and discharged from the institution, data collected will be audited by the primary and co-investigators. Two additional audits will occur: one after 5 subjects collected and one after 10 subjects collected. If these audits reveal any discrepancies, additional audits will be performed on an as needed basis.

11.0 DATA AND SAFTY MONITORING

The study drug will be given by FDA approved dosing and used within label as perioperative hypotension (when systematically addressed as noted above) is a form of distributive shock. As with all FDA approved medications, adverse events are reported. Patients will be monitored according to standard monitoring for patients in the perioperative transplant and collection of ADE will focus on those found in clinical studies using Ang II (Giapreza). The safety endpoints that will be captured will include: incidence of intraoperative arrhythmias for those who receive study drug intraoperatively (confirmed via EKG, flowsheet, or note documentation), incidence of postoperative arrhythmias occurring while receiving study drug postoperatively (confirmed via EKG, flowsheet, or note documentation), incidence of digital or other peripheral/visceral ischemia occurring during hospitalization for kidney transplant (as noted in chart documentation), incidence of venous or arterial thrombosis occurring during the hospitalization for kidney transplant (captured by ultrasound or other diagnostic imaging), incidence of thrombocytopenia while receiving study drug (as defined as platelet count < 50,000), incidence of post-operative fungal infections prior to discharge (as documented by the clinical care team), incidence of delirium while receiving study drug (as documented by the clinical care team), incidence of insulin infusion utilization while receiving study drug, pH values in the ICU at 24hrs, 48hrs, and 72hrs (if available). All of the noted safety variables above are routinely monitored for as part of ICU care.

The researchers will assess relatedness of the event to the study drug and will make every attempt to obtain enough information about the event to do so. Relationship of any AE to the use of study drug will be based on available information, using the following definitions:

Not Related: Another cause of the event is most plausible; and/or a clinically plausible temporal sequence is inconsistent with the onset of the event relative to initiation of study drug; and/or a causal relationship is considered biologically implausible.

Possibly Related: An event that follows a reasonable temporal sequence from administration of the Ang II (Giapreza) and in the investigators estimation follows a response pattern to the drug, but that could readily have been produced by a number of other factors.

Probably Related: An event that follows a reasonable temporal sequence from administration of the Ang II and there is a biologically plausible mechanism for Ang II (Giapreza) to cause or contribute to the AE and the event could not be reasonably explained by the known characteristics of the participant's clinical state.

For reporting purposes, both 'Possibly Related' and 'Probably Related' will be considered **Related**.

Adverse events will also be graded by severity according to CTCAE criteria.

- -Grade 1: Mild; Asymptomatic or mild symptoms; clinical or diagnostic observations only; intervention not indicated.
- -Grade 2: Moderate; Minimal, local or noninvasive intervention indicated; limiting age-appropriate instrumental activities of daily living.
- -Grade 3: Severe; Medically significant but not immediately life-threatening; hospitalization or prolongation of hospitalization indicated; disabling; limiting self-care activities of daily living.
- -Grade 4: Life-threatening consequences; urgent intervention indicated.
- -Grade 5: Death related to AE.

Given this is a clinical trial a Data Safety Monitoring Board (DSMB) will be established. This board will be composed of two Critical Care Pharmacists ([name] and [name]) with intimate knowledge of Ang II (Giapreza), vasopressors, Ang II (Giapreza) safety endpoints and no relationship to the conduct of the trial. This DSMB will review the safety endpoints collected above after 5, 10, 15, and 20 subjects are enrolled. They will be provided a Safety Summary Report for the allotted number of patients with "Relatedness" and Grading of captured ADE as described above.

Study Halting Criteria: For existing participants study drug will halt dosing immediately until further safety analysis and assessment by the DSMB can be completed and no further enrollment will take place until approved by the DSMB. The halting criteria are as follows:

- Two participants experience the same Grade 4 adverse event considered related to study drug
- 20% of the participants at time of analysis experience the same Grade 3 adverse event
- One participant experiences a Grade 5 AE considered related to study drug

Study can be restarted if the DSMB says it is okay to continue.

Subjects can withdraw from the study at any time. This withdrawal will not impact any portion of their care other than not being able to receive the study drug as it is not formulary approved at our institution. If a patient withdraws, their data will not be collected or used for analysis. Confidentiality will be maintained by using password protection for the Excel sheets, password protection for the computers used for storage of those Excel sheets, storing the sheet on the University H firewall behind the firewall and storing de-identified data within Redcap.

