Patients will be monitored according to standard monitoring for patients in the peri-operative transplant and collection of ADE will focus on those found in clinical studies using Ang II (Giapreza). The safety endpoints that will be captured will include: incidence of intraoperative arrhythmias for those who receive study drug intraoperatively (confirmed via EKG, flowsheet, or note documentation), incidence of postoperative arrhythmias occurring while receiving study drug postoperatively (confirmed via EKG, flowsheet, or note documentation), incidence of digital or other peripheral/visceral ischemia occurring during hospitalization for kidney transplant (as noted in chart documentation), incidence of venous or arterial thrombosis occurring during the hospitalization for kidney transplant (captured by ultrasound or other diagnostic imaging), incidence of thrombocytopenia while receiving study drug (as defined as platelet count < 50,000), incidence of post-operative fungal infections prior to discharge (as documented by the clinical care team), incidence of delirium while receiving study drug (as documented by the clinical care team), incidence of insulin infusion utilization while receiving study drug, pH values in the ICU at 24hrs, 48hrs, and 72hrs (if available). All of the noted safety variables above are routinely monitored for as part of ICU care.

Data Management

All patients that provide informed consent and receive Ang II (Giapreza) will have their data extracted. These patients will be considered included and associated with an alpha-numeric code that is linked to their medical record number (MRN). This list will be kept in a password protected Excel file on the primary investigator's computer stored on the H drive behind the University firewall on the primary investigator's password protected computer in a locked office. It will be available only to the co-investigators. Lastly, all data collected will not contain PHI and will be stored in Redcap.

All patients that provide informed consent but DO NOT receive Ang II (Giapreza) will be considered a screening failure and NO data will be extracted and they will not be associated with an alpha-numeric code linked to their MRN.

Records retention:

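### Postoperative arrhythmia, thrombocytopenia, delirium and insulin infusion are counted only while Ang II is running, so a related event after the infusion stops falls outside these four safety endpoints

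*Combined protocol and SAP*

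**What the plan says.** Sections 6.0 (Safety data points) and 11.0 list the safety endpoints in the same words. Four are tied to time on drug:

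- "incidence of postoperative arrhythmias occurring while receiving study drug postoperatively"
- "incidence of thrombocytopenia while receiving study drug (as defined as platelet count < 50,000"
- "incidence of delirium while receiving study drug (as documented by the clinical care team"
- "incidence of insulin infusion utilization while receiving study drug"

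Others in the same list are not. Ischemia and thrombosis are counted during the transplant hospitalization. Fungal infection is "incidence of post-operative fungal infections prior to discharge (as documented by the clinical care team". pH is read in the ICU at 24, 48 and 72 hours. Intraoperative arrhythmia is defined by who received drug in the operating room: "incidence of intraoperative arrhythmias for those who receive study drug intraoperatively". No reason is given for the different windows.

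Section 3.0 makes safety the secondary objective, measured by the incidence of common adverse events known from other Ang II studies, and gives no window. Section 1.0 puts safety in the primary objective. Section 11.0 adds a general provision, "Relationship of any AE to the use of study drug will be based on available information", and the DSMB reviews the listed endpoints after 5, 10, 15 and 20 subjects are enrolled.

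**The concern.** An endpoint that stops counting when the infusion stops measures on-infusion risk. That is a legitimate quantity, but it is narrower than the incidence after exposure to the drug. The relatedness definitions in Section 11.0 look at timing from initiation or administration of Ang II and do not require a running infusion. An event can therefore be judged related to the drug and still fall outside the endpoint that names it.

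The restriction bites hardest in patients with short infusions. Under Section 6.0, Ang II continues into the ICU only if it could not be titrated off during surgery. A patient weaned in the operating room and not restarted cannot contribute a postoperative arrhythmia and, realistically, cannot contribute delirium, although that patient was exposed.

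At stake is what a low or zero count means in the final report and in the DSMB Safety Summary Report.

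**Working it through.** **1. Is there another data item that would pick the event up?** I compared the four endpoints with the data lists in Section 6.0.

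| Endpoint | Window | Other item in the data lists |
|---|---|---|
| Delirium | on drug | none |
| Thrombocytopenia | on drug | none; no platelet count listed |
| Insulin infusion | on drug | none; no glucose or insulin item, only diabetes as a baseline comorbidity |
| Postoperative arrhythmia | on drug | partial: "Postoperative HR (bpm) every 1 hour for first 72 hours or duration of vasopressors (whichever is longer) after transplant", which gives rate, not rhythm |

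Duration of Ang II is a listed item, so the length of each patient's counting window will be known. Event onset is not listed.

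**2. Could pre-existing events be counted as new?** This acts in the opposite direction. Intraoperative arrhythmia is not limited to onset after Ang II start. The baseline list holds a history of arrhythmia and heart rate, but no rhythm at drug start. The CBC at transplant clearance and the neutrophil exclusion criterion imply earlier blood counts, but no pre-drug platelet count is a study data item.

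**3. Size.** The plan gives no figure for this point. Its only related arithmetic is enrolment: 20 treated / 0.50 vasopressor use = 40 consented, which reproduces. Everything below is illustration. Let p be the incidence from Ang II start to discharge, and q the share of affected patients whose event falls on infusion. Both are assumed, and new events only are considered. The on-infusion risk is then p × q.

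*Upper limit after 0 of 20.* One-sided 95%: 1 − 0.05^(1/20) = 0.139 for on-infusion risk. For incidence to discharge, divide by q:

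| q | 100% | 75% | 50% | 25% |
|---|---|---|---|---|
| Upper limit to discharge | 13.9% | 18.5% | 27.8% | 55.6% |

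*Chance of counting no event in 20*, (1 − p × q)^20:

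| p | q = 100% | 75% | 50% | 25% |
|---|---|---|---|---|
| 4% | 44% | 54% | 67% | 82% |
| 10% | 12% | 21% | 36% | 60% |
| 20% | 1% | 4% | 12% | 36% |

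The 4% is the reporting threshold quoted in Section 7.0, not an estimate for this population; 10% and 20% are assumed. At q = 100% nothing is lost. At 4% a zero count comes mainly from n = 20; the window matters more for commoner events.

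**4. Side effect of a wider count on the halting criteria.** At the first review, one event in 5 is 20%, which meets the Grade 3 criterion. Assume a background Grade 3 risk r to discharge for one event type, and q = 0.5.

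| Reading of 5 enrolled | r | On-infusion count | Count to discharge |
|---|---|---|---|
| 5 treated | 5% | 1 − 0.975^5 = 12% | 1 − 0.95^5 = 23% |
| 5 treated | 10% | 1 − 0.95^5 = 23% | 1 − 0.90^5 = 41% |
| 5 consented, half treated | 5% | 1 − 0.9875^5 = 6% | 1 − 0.975^5 = 12% |
| 5 consented, half treated | 10% | 1 − 0.975^5 = 12% | 1 − 0.95^5 = 23% |

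The consented reading follows Section 5.0 (20 treated of 40 consented). There, one event is 20% of 5 and more than 20% of the 2 or 3 treated, so the criterion is met with either denominator.

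**The case against.** The strongest reply is that late events are not lost. Section 11.0 says collection will focus on the listed events, which is not exclusive. Relatedness applies to any AE, and judging it already requires onset relative to drug start. The DSMB receives relatedness and grading of captured events, and the halting criteria speak of adverse events rather than of these endpoints. This stands. A reader might infer that post-infusion events go unrecorded, and the documents do not support that. What remains is that no AE collection period is stated and the named endpoints exclude such events.

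Second, Section 3.0 states no window, so it does not expressly ask for incidence after exposure; Sections 6.0 and 11.0 supply the windows. This also stands. The point is a gap between an open objective and narrow endpoints, not a breach of a stated target. Nor do the mixed windows spoil a planned analysis, since no comparison across event types is planned.

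Third, in an uncontrolled convenience sample of 20, an on-infusion window keeps out background events. That is a real advantage and a reason to keep the on-infusion count, though the documents do not offer it as their reason.

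Fourth, the illustrations rest wholly on assumed values, with one q applied to four different events. A reader might take 55.6% as an estimate of hidden risk; it follows solely from setting q = 25%.

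**Conclusion.** The concern holds as a limit on what the four endpoints measure. They are valid for on-infusion risk. Apart from pre-existing events, they cannot exceed incidence to discharge and may understate it. Three of the four (delirium, thrombocytopenia, insulin infusion) have no other data item, and arrhythmia has a partial one. A reader might single out delirium and thrombocytopenia as the only clear gaps, but the data lists do not support that ranking, because insulin infusion is equally uncovered.

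The size is unknown and could be nil if all onsets fall on infusion. The conclusion rests on the wording of Sections 3.0, 6.0 and 11.0, not on the illustrative figures. This is a low-cost improvement, not an error that invalidates the safety data.

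**What to change.** In Sections 6.0 and 11.0, for these four endpoints:

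- Keep the on-infusion count and add a count of events with onset from Ang II start to discharge.
- Make onset date and time a data item.
- Report both counts with infusion duration, including in the DSMB Safety Summary Report.
- Record the last platelet count before Ang II, and flag arrhythmias with onset before Ang II start, so that pre-existing events are not counted as new.

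The ischemia, thrombosis and fungal infection windows can stay as they are.

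Before the added count is introduced, the sponsor and DSMB should reconcile which window the Grade 3 halting criterion uses, since the text does not say. If it already covers any Grade 3 AE in any window, the added count changes nothing. If it uses the on-infusion endpoints and were moved to the wider count, the chance of meeting it would rise as in step 4.

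The cost is wording in two sections, an onset field, a platelet field, an arrhythmia flag and some added chart review; charts are already read to discharge for other endpoints. There are two downsides. A single-arm study of 20 will pick up more background events. Ascertainment will also be less even after the ICU, because the protocol describes routine monitoring of these variables only within ICU care, so the report should say so.
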